720 newly diagnosed T2DM subjects (less than 2 years) in good general health as determined by physical exam, medical history, blood chemistries, CBC, TSH/free T4/total T4, lipid profile, urinalysis, and EKG will take part in the study. Subjects must have a HbA_{1c} > 6.5% and must not have taken any oral or injectable antidiabetic medication for more than 2 days, except metformin, and must not be taking any medications known to affect glucose homeostasis. Only subjects whose body weight has been stable (\pm 3lbs) over the preceding three months and who do not participate in an excessively heavy exercise program will be included. Individuals with evidence of proliferative diabetic retinopathy, albuminuria >300 mg/dl, symptomatic diabetic neuropathy, or history of cardiovascular disease (class III-IV CHF) will be excluded. Subjects with AST or ALT greater than 3.5-fold above the upper limit of normal will be excluded. All subjects must be GAD antibody negative. Subjects meeting these criteria will meet with a dietitian and be instructed in a weight maintaining diet containing 50% carbohydrate, 30% fat, and 20% protein. They also will receive instructions about a modest intensity exercise program (40 minutes of walking 3-4 times per week). After one week on the diet, all subjects will receive: (1) oral glucose tolerance test; (2) hyperglycemic clamp-will be performed in a subgroup of 50 subjects (25 in each group) to provide a measure of beta cell function; (3) DEXA for total body fat content/fat distribution; (4) carotid ultrasound-for measurement in carotid intima media thickness; (5) fundus examination; (6) 24-hour urine for albumin and creatinine; (7) ankle arm blood pressure measurement.

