
1) Subjects with type 2 diabetes diagnosed in the past 2 years 2) subjects must be on diet or metformin only 3) age 18-75 years 4) must be in general good health and without a major organ disease 5) must have creatinine < 1.5 6) must have LFT < twice the upper normal limit 7) subjects must have HbA1c > 6.5%
	
(2)	Identify the criteria for exclusion:

1) subjects with type 1 diabetes or positive for anti diabetic antibodies 2) subjects with type 2 diabetes who were diagnosed more than 2 years or who receive insulin or pharmacological therapy other than metformin 3) subjects with a cardiovascular event in the past year
	
(3)	
Recruitment Describe plans how the population will be identified for the purpose of recruiting. (Consider HIPAA Waiver if needed to allow those without existing legitimate access to PHI to use it to identify potential subjects.) (e.g., database search, personal contacts, referrals, patients under the care research team, etc.)

Advertising material will be posted in the medical center and near by hospitals or in primary care offices (advertising material is included for IRB approval). Subjects interested in participating in the study will be asked to contact one of the investigators. We also have access to TDI patient database that can search and select patients that are newly diagnosed diabetic patients or have diabetes markers such as HbA1c . We are planning on identifying such potential subjects and then contacting their health care providers for referral. We will send out "dear Doctor" letter informing the providers about our research study and ask them to contact participants. The treating physician will be making the initial patient contact, not the researcher. If the patient is interested, then either the patient will contact the PI or, with the permission of the patient, the PI will be invited to talk with the patient about study participation.
	
(4)	
Recruitment Describe how initial contact will be made with potential subjects. Describe how those making initial contact have a legitimate access to the subjects' identity and the subjects' information. (Consider HIPAA Waiver if needed to disclose PHI to individuals who would not have otherwise had legitimate access.)

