- 7) **EUGLYCEMIC INSULIN CLAMP** On a separate day, subjects will be admitted to the CRC 6:45 and 8 AM for a four-hour, two-step hyperinsulinemic euglycemic insulin (20 and $80 \text{ mU/m}^2 \cdot \text{min}$) clamp with a prime-continuous infusion of $3\text{-}^3\text{H}\text{-glucose}$. The $3\text{-}^3\text{H}$ glucose prime will be $25 \mu\text{Ci} \times$ (fasting plasma glucose/100); the continuous infusion will be given at the rate of $0.40 \mu\text{Ci/min}$ for 240 minutes. Plasma samples for tritiated glucose will be obtained at 5-15 minute intervals during the 30 minutes before and throughout the insulin clamp, to quantitate rates of whole body glucose disposal and suppression of endogenous (primarily hepatic) glucose production. Continuous indirect calorimetry (Deltatrac, Sensormedics, Anaheim, CA) will be performed for 30 minutes prior to the start of the insulin clamp, and during the 210-240 period of

the insulin clamp to calculate rates of glucose and lipid oxidation Total blood loss for the procedure is up to 160 ml.

8) **Fundus Examination:** All diabetic subjects seen at the Texas Diabetes Institute have an annual ophthalmologic examination as part of their routine care. The fundus photographs will be read blindly by University of Wisconsin-Madison, Department of Ophthalmology and Visual Sciences.

Following completion of these tests, subjects will be randomized (using a table of random numbers) to receive, in open label fashion, one of the following treatment regimens:

GROUP I: Group I will be started on pioglitazone (15 mg/day) plus metformin (1000 mg/day) with the supper meal and exenatide (5 mcg s.c. bid 30 min before breakfast and supper).

If, after month one, the FPG ≥ 110 mg/dl or HbA_{1C} $\geq 6.0\%$, the exenatide dose will be increased to 10 mcg bid, pioglitazone will be increased to 30 mg/day, and metformin to 1000 mg bid.

If, after month two, the FPG ≥ 110 mg/dl or HbA_{1C} $\geq 6.0\%$, pioglitazone will be increased to 45 mg/day. Subjects who will not tolerate 5 mg bid exenatide because of GI side effects will be started on lower dose (1 mg s.c bid 30 min before breakfast and supper): and the dose will be titrated up to the maximal tolerated dose.

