List each group exposed to this procedure on a separate line. (e.g., experimental, control, Arm A, Arm B, etc) Or state All Groups/Subjects		For each group, list the benefits of this procedure (either the procedure or a monitoring procedure likely to contribute to the subject's well being). If there are no benefits, state "none".
Group I	None	
Group II	None	
For this procedure or component, list the reasonably foreseeable risks List the risks according to the probability (likely, less likely or rare) and magnitude (serious or not serious). (include: 1) expected adverse events; 2) rare and serious adverse events; 3) all other psychological, social, legal harms)		
Likely These risks are expected to occur in more than 20 [or insert different #] out of 100 subjects.	Not serious	Serious
	
 None 	
 None
Less likely These risks are expected to occur in 5 - 20 [or insert different range] subjects or less out of 100 subjects.	Not serious	Serious
	
 none 	None
Rare These risks are expected to occur in less than 5 [or insert different #] subjects out of 100	Serious	
	Local reaction at iv site Total blood loss for the procedure is up to 88 ml.	
 none
Are all groups exposed to the risks listed above?  Yes  No  N/A (There is only one group) If No, Describe: [Describe here]		

Procedure or component 2 DEXA		
List each group exposed to this procedure on a separate line. (e.g., experimental, control, Arm A, Arm B, etc Or state All Groups/Subjects		For each group, list the benefits of this procedure (either the procedure or a monitoring procedure likely to contribute to the subject's well being). If there are no benefits, state "none".
GROUP I	NONE	
GROUP II	NONE	
For this procedure or component, list the reasonably foreseeable risks List the risks according to the probability (likely, less likely or rare) and magnitude (serious or not serious). (include: 1) expected adverse events; 2) rare and serious adverse events; 3) all other psychological, social, legal harms)		
Likely These risks are expected to occur in more than 20 [or insert different #] out of 100 subjects.	Not serious • Radiation exposure (6 mrems). Although we cannot be sure that nothing will happen from such a small amount of radiation, we know that any risk is very small.	Serious None

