List each group exposed to this procedure on a separate line. (e.g., experimental, control, Arm A, Arm B, etc Or state All Groups/Subjects		For each group, list the benefits of this procedure (either the procedure or a monitoring procedure likely to contribute to the subject's well being). If there are no benefits, state "none".	
GROUP I		NONE	
GROUP II		NONE	

For this procedure or component, list the reasonably foreseeable risks
 
List the risks according to the probability (likely, less likely or rare) and magnitude (serious or not serious). (include: 1) expected adverse events; 2) rare and serious adverse events; 3) all other psychological, social, legal harms)
			
Likely These risks are expected to occur in more than 20 [or insert different #] out of 100 subjects.		Not serious 
none	Serious None
Less likely These risks are expected to occur in 5 - 20 [or insert different range] subjects or less out of 100 subjects.		Not serious None	Serious 
none
Rare These risks are expected to occur in less than 5 [or insert different #] subjects out of 100		Hypoglycemia Local reaction at iv sites Total blood loss for the procedure is up to 160 ml.	Serious none
Are all groups exposed to the risks listed above?  Yes  No  N/A (There is only one group) If No, Describe: [Describe here]			

Procedure or component 7 Fundus examination			
List each group exposed to this procedure on a separate line. (e.g., experimental, control, Arm A, Arm B, etc Or state All Groups/Subjects		For each group, list the benefits of this procedure (either the procedure or a monitoring procedure likely to contribute to the subject's well being). If there are no benefits, state "none".	
GROUP I		NONE	
GROUP II		NONE	

For this procedure or component, list the reasonably foreseeable risks
 
List the risks according to the probability (likely, less likely or rare) and magnitude (serious or not serious). (include: 1) expected adverse events; 2) rare and serious adverse events; 3) all other psychological, social, legal harms)
			
Likely These risks are expected to occur in more than 20 [or insert different #] out of 100 subjects.		Not serious	Serious
		
 • none 	None
Less likely These risks are expected to occur in 5 - 20 [or insert different range] subjects or less out of 100 subjects.		Not serious	Serious

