List each group exposed to this procedure on a separate line. (e.g., experimental, control, Arm A, Arm B, etc) Or state All Groups/Subjects		For each group, list the benefits of this procedure (either the procedure or a monitoring procedure likely to contribute to the subject's well being). If there are no benefits, state "none".
GROUP II		This drug combination is likely to reduce your blood sugar
For this procedure or component, list the reasonably foreseeable risks List the risks according to the probability (likely, less likely or rare) and magnitude (serious or not serious). (include: 1) expected adverse events; 2) rare and serious adverse events; 3) all other psychological, social, legal harms)		
Likely These risks are expected to occur in more than 20 [or insert different #] out of 100 subjects.		Not serious 
 • Hypoglycemia • Weight gain Serious None
Less likely These risks are expected to occur in 5 - 20 [or insert different range] subjects or less out of 100 subjects.		Not serious 
 • Abdominal pain • vomiting Serious 
 • none
Rare These risks are expected to occur in less than 5 [or insert different #] subjects out of 100		none Serious none
Are all groups exposed to the risks listed above?  Yes  No  N/A (There is only one group) If No, Describe: [Describe here]		

7. Safety Precautions. (The study should at a minimum describe safeguards to address the serious risks listed above.)

(1) Describe the procedures for protecting against or minimizing any potential risks for each of the research procedures listed above.

PROTECTION OF SUBJECTS. The PI will review all results on a weekly basis to ensure that the timeliness and conformity with established clinical monitoring of the subjects is followed.

1. Any subject with clinically significant cardiac, pulmonary, gastrointestinal, or endocrine (other than diabetes) disease will be excluded from study.
2. Prior to study, a venous hematocrit will be obtained. Volunteers with a hematocrit less than 34 vol % will be excluded from the study.
3. Any serious adverse event will be reported to the IRB within 24 hours. All non-serious adverse events will be reported by the investigator to the IRB within 72 hours. An annual report summarizing all adverse events will be submitted to the IRB.

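### Women are eligible from age 18 with no pregnancy or breast-feeding criterion or test, and the euglycemic clamp risk table omits its radioactive tracer

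*Combined protocol and SAP*

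**What the plan says.** Eligibility is set out in three places.

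- Section 4 gives seven inclusion and three exclusion criteria. Age is "age 18-75 years" and sex is not restricted. The exclusions cover diabetes type and antibodies, duration and prior drug treatment, and "subjects with a cardiovascular event in the past year".
- Section 3 adds further exclusions, beginning "Individuals with evidence of proliferative diabetic retinopathy, albuminuria >300 mg/dl, symptomatic diabetic neuropathy, or history of cardiovascular disease", and requires body weight stable within 3 lb over the preceding three months. Its health screen is a physical exam and "medical history, blood chemistries, CBC, TSH/free T4/total T4, lipid profile, urinalysis, and EKG will take part in the study".
- Section 7 excludes other significant organ disease and sets a blood-count limit: "Volunteers with a hematocrit less than 34 vol % will be excluded from the study".

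On radiation, section 3 gives DEXA to all subjects at baseline, and section 6a repeats it at three years and in the extended follow-up. The DEXA table in section 6c puts 6 mrem under likely, non-serious risks and adds a caution: "Although we cannot be sure that nothing will happen from such a small amount of radiation". Section 6a, item 7, describes a four-hour, two-step euglycemic "clamp with a prime-continuous infusion of" tritiated glucose, dosed in microcuries. The section 6c table for that clamp (component 6) lists hypoglycemia, then "Local reaction at iv sites Total blood loss for the procedure is up to 160 ml". Its other risk cells say none.

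**The concern.** There are two linked gaps. First, the plan schedules ionizing radiation for every subject and a radioactive tracer for some, in a population that includes women of child-bearing age. Yet no written criterion or test asks about pregnancy or breast-feeding. Section 4 has staff question candidates by telephone against the listed criteria, so an item missing from the list gives them no prompt to ask.

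Second, the plan treats radiation as a reportable risk for DEXA but leaves it out for the one other research procedure whose method specifies a radioactive dose. The section 6c form asks for foreseeable risks procedure by procedure, so anyone who relies on the component 6 table would not learn that the clamp involves radioactivity.

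At stake are the possible exposure of a fetus or a breast-fed infant that the plan never considered, and a risk disclosure that does not match the plan's own methods.

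**Working it through.** **Eligibility.** I took each rule that might stand in for a pregnancy criterion.

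- Age and sex: there is no upper or lower limit specific to women. The Cox model in the Data Analysis section adjusts for sex, so both sexes are expected.
- Screening tests: chemistries, blood count, thyroid tests, lipids, urinalysis and EKG are itemized. A pregnancy test is not.
- Good general health and no major organ disease: pregnancy is neither named nor an organ disease.
- Weight stable within 3 lb for three months: this bears most directly on the question and would be expected to remove many established pregnancies. It looks backward from entry only. Very early pregnancy and breast-feeding can pass it, and it does not apply again before the repeat DEXA scans.

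No other supplied section closes these three openings.

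**Tracer activity per euglycemic clamp.** The plan states no total to reproduce. The inputs from section 6a, item 7, are a prime of 25 microcuries × (fasting plasma glucose/100) and an infusion of 0.40 microcuries/min for 240 minutes. Fasting glucose is not given for this purpose. I assume 100 to 200 mg/dl.

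Total = 25 × FPG/100 + 0.40 × 240

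- Infusion: 0.40 × 240 = 96 microcuries
- FPG 100: 25 + 96 = 121 microcuries
- FPG 150: 37.5 + 96 = 133.5 microcuries
- FPG 200: 50 + 96 = 146 microcuries

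**Number of clamps.** Section 6b lists two euglycemic clamps and none afterwards. Section 10 pays clamp participants for two insulin sensitivity tests, before and at the end of treatment, which I read as this clamp. Against that, the list of tests repeated at three years in section 6a names the hyperglycemic clamp but not the euglycemic one. If there are two, at the same fasting glucose each time, the total is 2 × 121 = 242 to 2 × 146 = 292 microcuries per participant.

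**Number of subjects.** Section 3 assigns the hyperglycemic clamp to 50 subjects (25 per group), but that procedure has no tracer. The euglycemic clamp is absent from the section 3 test list and its number is not stated. Section 10 suggests that clamp participants have both tests, so 50 is a plausible inference, not a documented figure.

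**Risk tables compared.** DEXA is tabled with its radiation of 6 mrem. The euglycemic clamp, at 121 to 146 microcuries by the plan's own formula, is tabled with none. The two units cannot be compared, because the documents give no conversion to a radiation dose.

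**The case against.** The strongest reply is that existing rules and contacts already do much of this work. Weight stability, physical exam, medical history, the telephone screen and the investigator interview would in practice catch many pregnancies. That stands as far as it goes, and a reader should not infer that a pregnant woman with raised HbA1c satisfies every entry rule, or that anyone aged 18 to 75 may enter. The documents do not support either reading. What remains uncovered is early pregnancy, breast-feeding, and pregnancy arising during years of follow-up.

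A second reply is that the consent form may already cover pregnancy and radiation. It may: consent pages are not in the supplied text, so no one should infer that they are silent. But consent wording would not complete the eligibility lists or the component 6 table, both of which are in the text.

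A third is timing. The document carries a 2019 approval date, recruitment was planned for the first year, the statistical section is written in the past tense, and section 6b schedules no further euglycemic clamps. This suggests, without proving it, that a check before the first DEXA or tracer dose would now affect few subjects. Repeat DEXA would then be the main practical use of the check, and the risk table would still need completing.

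**Conclusion.** The point holds as a cheap improvement. The eligibility lists lack a pregnancy and breast-feeding criterion or test while DEXA is given to all subjects. The component 6 table is incomplete because it omits a tracer exposure of about 121 to 146 microcuries per euglycemic clamp. That range rests on assumed fasting glucose of 100 to 200 mg/dl and the stated 240-minute infusion. Doubling it rests on sections 6b and 10, with which the three-year repeat list in section 6a does not fully agree.

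Three larger inferences are tempting and unsupported. One is that every clamp subject receives tracer: it belongs to the euglycemic clamp only. Another is that the undeclared exposure is large or exceeds that of DEXA: without a conversion, its size in mrem is unknown. The last is that pregnancies would distort HbA1c or the other endpoints enough to need an analysis rule. The documents give no number of women who might be affected and no effect can be shown, so the case rests on safety and disclosure.

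**What to change.** Make three edits.

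- In section 4, add pregnancy and breast-feeding to the exclusions. Check pregnancy by a urine test, and ask about breast-feeding, before any DEXA or tracer dose, including repeat scans.
- In the component 6 table of section 6c, add tracer radiation with the total microcuries per clamp. Reconcile the number of euglycemic clamps between sections 6a, 6b and 10 so that the cumulative figure is right.
- Confirm that the consent form matches both changes, and amend it only if it does not.

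The cost is amendment wording and a urine test in the relevant women. Screening already includes a urinalysis and the baseline tests a 24-hour urine collection, so little is added. A few candidates would become ineligible. Randomization, the endpoints and the sample size are unaffected.

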Following completion of these tests, subjects will be randomized (using a table of random numbers) to receive, in open label fashion, one of the following treatment regimens: (i) Group I will be started on pioglitazone (15 mg/day) plus metformin (1000 mg/day) with the supper meal and exenatide (5 mcg s.c. bid 30 min before breakfast and supper) and up-titrated to 45 pioglitazone plus 2000 metformin and 10 mcg s.c. bid exenatide to achieve HbA1c <6.0%; (II) Group II will be started on metformin, 1000 mg with breakfast and 1000 mg with supper, glyburide and basal insulin will be added and up titrated to achieve HbA1c <6.0% Subjects will be recruited during the first year and followed up for additional two years. After completing the repeat studies, subjects will be asked to continue in the study and with the study medications without any change. Follow up visits will occur every 3 months) until the last patient recruited into the study completes 2 –years of follow-up. At the Follow visit Fasting Glucose and HbA1C will be performed. At the annual visits blood work to check the following: fasting glucose, HbA1C, and other repeat labs. Every 2 years or if the subject decides to discontinue participation, we will repeat the annual labs, OGTT, eye photographs, and carotid ultrasound.

4. Study Population(s).

You will be drawing subjects from one or more populations. In medical research, for example, a population can be individuals with type 2 diabetes controlled with diet, or a population of healthy individuals. In social behavioral research, a population can be individuals attending an education program, etc.

- a. How many different populations are you enrolling in this study?
- b. For each different population, provide a short descriptive label: (e.g., *normal-healthy, diabetics, patients needing surgery, parents, child, etc.*)

1

720 Newly diagnosed type 2 diabetic subjects
Will be enrolled to have 600 completers .

For each **specific** population identified 4b, provide the following information in the table provided below. (**One table is provided, use copy and paste for additional tables if enrolling more than one population.**)

Population # [Type # given to population in 4b]	Population Descriptive Label: [Insert short label from 4b] Enrollment of [Insert #] requested to obtain [Insert #] completers.
XCheck here if enrolling only one population	
(1)	Identify the criteria for inclusion :

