If, at any time after achieving a HbA_{1C} $\leq 6.0\%$, the HbA_{1C} rises above 6.0% and the subject is on submaximal doses of metformin or pioglitazone or exenatide, the medication(s) will be titrated up to the maximally effective dose and the subject will not be considered a treatment failure.

If, after month six, the HbA_{1C} $\geq 6.0\%$ and the subject is on maximum doses of all triple therapy medications, the subject will be considered a treatment failure. If, after month 6, the HbA_{1C} rises to $> 6.5\%$, bedtime glargine insulin (10-20 units) will be started and titrated to a maximum of 60 units to achieve a FPG < 110 mg/dl and HbA_{1C} $< 6.0\%$. If more than 60 units of glargine insulin is required to reduce the HbA_{1C} $< 6.5\%$, regular insulin will be added to each meal and adjusted based upon the pre- and post-meal blood glucose levels. These "treatment failure" subjects will continue with all follow up visits/procedures. Throughout the titration process, downward adjustments will be allowed for the development of hypoglycemia, as defined by a blood glucose less than 60 mg/dl with (symptomatic hypoglycemia) or without (asymptomatic hypoglycemia) symptoms. Serious hypoglycemia is defined as any hypoglycemic reaction requiring assistance from a third party for recovery.

GROUP II: Group II will be started on metformin, 1000 mg with breakfast and 1000 mg with supper.

If, after month one, the FPG ≥ 110 mg/dl or HbA_{1C} $\geq 6.0\%$, glipizide (5 mg) will be added: 1-2 tablets with breakfast depending on the FPG, HbA_{1C}, and discretion of the investigator in order to avoid hypoglycemia.

If, after month two, the FPG ≥ 110 mg/dl or HbA_{1C} $\geq 6.0\%$, the glipizide dose will be increased to 4 tablets (20 mg/dl).

If, after month three, the FPG > 110 mg/dl or HbA_{1C} $> 6.0\%$, bedtime basal insulin (10-20 units) will be started and titrated up to achieve a FPG < 110 mg/dl or HbA_{1C} $< 6.0\%$

If, at any time after achieving a HbA_{1C} $< 6.0\%$, the HbA_{1C} rises above 6.0% and the subject is on submaximal doses of metformin or glipizide or glargine insulin, the medication(s) can be titrated up to the maximally effective dose and the subject will not be considered a treatment failure.

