		None	
 • none
Rare These risks are expected to occur in less than 5 [or insert different #] subjects out of 100		none	Serious
			none
Are all groups exposed to the risks listed above?  Yes  No  N/A (There is only one group) If No, Describe: [Describe here]			

Procedure or component 8

Pharmacological Therapy with metformin, and pioglitazone plus exenatide

List each group exposed to this procedure on a separate line. (e.g., experimental, control, Arm A, Arm B, etc Or state All Groups/Subjects	For each group, list the benefits of this procedure (either the procedure or a monitoring procedure likely to contribute to the subject's well being). If there are no benefits, state "none".	
GROUP I	This drug combination is likely to reduce your blood sugar	

For this procedure or component, list the reasonably foreseeable risks
 
List the risks according to the probability (likely, less likely or rare) and magnitude (serious or not serious). (include: 1) expected adverse events; 2) rare and serious adverse events; 3) all other psychological, social, legal harms)
		
Likely These risks are expected to occur in more than 20 [or insert different #] out of 100 subjects.	
Not serious
 
 • Nausea (exenatide) • Weight gain (pioglitazone) • Anemia (pioglitazone) 
Itching where Exenatide once weekly (Bydureon) was injected
 
 • Feeling tired (lack of energy or tiredness) • Injection site events (for example: lumps, hardening at the site of injection, bruising, redness of skin, itching, rash, and/or pain) 	Serious None
	Not serious	Serious

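### The rule for exenatide-intolerant Group I subjects prints mg for mcg, so its lower dose reads as 100 times the scheduled maximum

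*Combined protocol and SAP*

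**What the plan says.** Exenatide is dosed in two places. Section 3 (Study Design) starts Group I at 5 mcg twice daily and titrates to "10 mcg s.c. bid exenatide to achieve HbA1c <6.0" percent. The Group I algorithm in Section 6a repeats the start, "exenatide (5 mcg s.c. bid 30 min before breakfast and supper", and its month-one step says "the exenatide dose will be increased to 10 mcg bid".

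The month-two paragraph of the same algorithm then gives the rule for intolerance: "Subjects who will not tolerate 5 mg bid exenatide because of GI side effects will be started on lower dose (1 mg s.c bid", taken before the same two meals. From there, "the dose will be titrated up to the maximal tolerated dose".

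The Group II algorithm adds glipizide as 5 mg tablets. Its month-two step reads "the glipizide dose will be increased to 4 tablets (20 mg/dl". Its basal-insulin step opens "If, after month three, the FPG > 110 mg/dl or" and continues with HbA1c above 6.0%. The same sentence sets the titration target as fasting plasma glucose (FPG) below 110 mg/dl or HbA1c below 6.0%. Section 3 and the Abstract state the Group II goal as HbA1c below 6.0%, with no FPG alternative.

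**The concern.** The intolerance rule is meant to lower the dose, but the printed number raises it far above anything in the schedule. It is operative text. Someone treating a subject with nausea or vomiting would turn to it, and the Section 6c risk table for the Group I drugs expects nausea with exenatide in more than 20 of 100 subjects. The unit should not have to be inferred.

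The rule may also still be in use. Under the Washout Phase text in Section 6a, conventional-arm participants with HbA1c above 7.5% at six years are switched to triple therapy. No exenatide dose is given there, so the Section 6a rule is the only specific intolerance instruction for these new starters.

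The Group II insulin wording raises a smaller question. Start and target are both joined by *or*, so one value can trigger insulin while the other already satisfies the target.

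**Working it through.** **Exenatide.** Inputs: start 5 mcg and maximum 10 mcg twice daily (Sections 3 and 6a); printed intolerance doses 5 mg and 1 mg twice daily (Section 6a). With 1 mg = 1000 mcg:

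| Printed dose | In mcg | Ratio to 5 mcg start | Ratio to 10 mcg maximum |
|---|---|---|---|
| 1 mg (the lower dose) | 1000 | 1000/5 = 200 | 1000/10 = 100 |
| 5 mg (the dose not tolerated) | 5000 | 5000/5 = 1000 | 5000/10 = 500 |

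These are ratios of printed doses, not exposures. If both units are read as mcg, the rule makes sense: a subject who cannot tolerate 5 mcg restarts at 1 mcg, 1/5 of the starting dose, and works up.

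**Could the unit be a text-reading fault?** Exenatide is dosed in mcg four other times, twice in Section 3 and twice in Section 6a, and mcg was read correctly each time. The micro symbol in the tracer doses of the euglycemic clamp, also in Section 6a, was read correctly too. A fault is therefore unlikely but not excluded.

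**Glipizide.** 4 tablets × 5 mg = 20 mg. The printed mg/dl is a concentration unit and cannot describe a tablet dose.

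**Group II basal insulin.** Ignoring exact ties at 110 mg/dl and 6.0%:

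| FPG | HbA1c | Insulin starts? | Section 6a target already met? | HbA1c goal of Section 3 and Abstract met? |
|---|---|---|---|---|
| below 110 | below 6.0% | no | yes | yes |
| below 110 | above 6.0% | yes | yes | no |
| above 110 | below 6.0% | yes | yes | yes |
| above 110 | above 6.0% | yes | no | no |

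Three states start insulin. Two of them already meet the Section 6a target, and one of those two (FPG below 110, HbA1c above 6.0%) conflicts with the goal in Section 3 and the Abstract.

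Example: FPG 105 mg/dl, HbA1c 6.4%. Insulin starts because 6.4 > 6.0, and the target is already met because 105 < 110. Mealtime insulin is not triggered, since 6.4 is not above 6.5. The Group II up-titration rule does not apply to a subject whose HbA1c has not yet been below 6.0%. The documents do not say how often this state occurs.

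**The case against.** The strongest reply is that the misprint refutes itself. The sentence speaks of a lower dose, taken twice daily, and the only twice-daily exenatide dose with the number 5 is 5 mcg. The 10 mcg ceiling is stated elsewhere. Section 7 adds telephone contact every two weeks after therapy starts and dose adjustment for severe side effects. All of this stands and lowers the practical risk. It does not make the printed dose right, and the intolerance sentence does not refer back to the 10 mcg ceiling.

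A reader might infer that a different product explains the unit, because the Section 6c risk table for Group I includes "Itching where Exenatide once weekly (Bydureon) was injected". The documents do not support this: the rule is for twice-daily dosing before meals, and Sections 3 and 6a give no dose for a once-weekly product.

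On Group II, other text still drives treatment. Section 3 and the Abstract set the HbA1c goal, Section 6a adjusts therapy every three months on HbA1c, FPG and home readings, and Section 7 calls for adjustment when control is inadequate. The start condition also stays true while HbA1c exceeds 6.0%. Group I joins its glargine targets with *and*, but that is not a like-for-like model: there insulin is added after month six once HbA1c exceeds 6.5%, whereas in Group II basal insulin is a routine step after month three. These points reduce the Group II matter to a query.

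**Conclusion.** The exenatide intolerance rule is wrong as written and should be corrected. The printed lower dose is 100 times the protocol's maximum and 200 times its start. This rests on the extracted text matching the source page, which one look will settle. The intended unit is almost certainly mcg. The glipizide unit is a second slip of the same kind, with an obvious correction.

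A reader might infer from the 100-fold figure that subjects were overdosed. The documents contain no record of any dose given under this rule, so that does not follow.

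The Group II target wording conflicts with the HbA1c goal stated elsewhere in the protocol, but only in one of the three states that start insulin. A reader might infer that the control arm was under-titrated and the primary HbA1c comparison tilted. The documents do not support that either: other provisions still direct titration, and the frequency of the conflicting state is unknown. No effect on any analysis is claimed.

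**What to change.** Check the source page. Then, with clinical confirmation, change the two doses in the Section 6a intolerance rule to 5 mcg bid and 1 mcg s.c. bid, and add after the titration clause that the dose is not to exceed 10 mcg bid. In the same edit, change the Group II glipizide unit from mg/dl to mg, so that four tablets read as 20 mg.

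Separately, ask the clinical team which target governs Group II basal insulin when FPG is below 110 mg/dl but HbA1c is above 6.0%, and record the answer. This review does not prescribe *and*: a stricter target may raise the risk of hypoglycemia, which Section 6c already expects in more than 20 of 100 Group II subjects. Stopping basal titration once FPG is at target is a legitimate choice if it is stated.

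The unit corrections cost a few words and an IRB notification, with no added procedures or patients. Any change to the insulin target alters treatment and needs clinical agreement. The 2019 approval date and the past tense of the statistical section suggest that much of the titration may be finished. For those subjects, a record of the unit and the insulin target actually followed is enough.
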